### Background

Some youth find it difficult to attend school. This may lead to absence, intermittent or continued, which jeopardizes academic development (Carroll, 2010) and often contributes to impaired social-emotional development (Malcolm, Wilson, Davidson, & Krik, 2003). Recurrent and prolonged school absenteeism is a complex problem with numerous causes (Havik et al., 2015) and risk factors (Ingul, Klöckner, Silverman, & Nordahl, 2012). It is also a major predictor for school drop-out (Calderon et al., 2009; Christle, Jolivet, & Nelson, 2007). Longer-term problems linked with school drop-out include unemployment, imprisonment, ill-health, and marital problems (Kearney, 2016).

Problematic school absenteeism (SA) has been defined by Kearney (2008) as: (1) having missed at least 25% of total school time for at least 2 weeks, (2) experienced severe difficulty attending classes for at least 2 weeks, with a significant interference in the young person's or family's daily routines, or (3) had more than 10 days (or 15 %) absence during any 15-week period in the school year. In this study, the definition by Kearney (2008) for problematic absenteeism is adapted. One advantage of this definition is that it allows for interventions with youths whose absence is sporadic but still problematic.

There has been considerable confusion on how to conceptualize School attendance problems (SAP). Terms such as truancy (TR) and school refusal (SR) have traditionally been used to describe different types of problematic school absenteeism (e.g Heyne, et al., 2019), and interventions have usually been designed for either TR or SR. Research indicate that groups overlap, and that diagnostic heterogeneity is considerable (Egger, Costello, & Angold, 2003).

In Norway, there are no official guidelines and records for registering absence in primary and secondary education. Therefore, few reliable measures of the proportion of children and youth with SA in Norway exists (Palmu et al., 2021). One study of 5465 pupils in 6th to 10th grade showed that 3,9 % had been absent for more than 10 days within the last 3 months, which qualify for SA, and 7.5% of the students were absent more than 8 days last 3 months, which constitute 13.3% of the schooldays (or more) (Havik et al., 2015). According to descriptions of school and health professionals, the proportion of young people with problematic SA seem to have augmented during the Covid-19-pandemic.

A recent meta-analysis of six psychosocial interventions for SR, five Cognitive Behavioural Treatment (CBT) trials and two medication plus CBT trials, showed a significant reduction in school absenteeism with a moderate effect size ( $g = .54$ ), but no significant effects on anxiety symptoms (B. Maynard et al., 2018). A systematic review of TR interventions found a moderate and significant mean effect-size,  $g = .46$  (average improvement in attendance of 4.69 days), but 15 of the 16 studies reported absence rates above 10% posttreatment (B. R. Maynard, McCrea, K. T., Pigott, T. D., Kelly, M. S., 2013) .

Researchers have called for an integrated and common perspective to the complex problem of school absenteeism, that take into consideration the multiple causes and risk factors, and both

personal, familial and school related factors that influence the individual youth (Kearney & Albano, 2004). There is a need for studies that develop and evaluate integrated and comprehensive interventions to problematic SA, which incorporate different treatment needs of this heterogeneous group (Kearney & Ross, 2014; Maynard et al., 2013). Few such studies exist, with one exception being the Back2School (B2S) study in Aarhus, Denmark ([name] et al., 2019). The Back2School (B2S) program is a modular trans-diagnostic CBT intervention aimed at increasing school attendance and decreasing psychological problems among youths with problematic SA. The Danish B2S study was a randomized controlled treatment trial comparing the effects of the B2S program against treatment as usual (N= 152; 60.5 % boys; 12.15 years mean age) (Lomholt et al., 2020; [name] et al., 2019). Results of the B2S study, indicated significant and positive effects on attendance rate from pre to 3-month follow-up ( $d = 0.73$ ) for the B2S condition, but with no significant difference when compared to the TAU condition ( $d = 0.60$ ) (Johnsen, Lomholt, Heyne, Jensen, Jeppesen, Silverman, & [name], 2020). The B2S study in Denmark faced challenges with the validity of measurements of school attendance and found insufficient correspondence between parental reports on absence data with official records data. This made the interpretation of results difficult. The B2S study found, however, that the youths in the B2S group had significantly larger reductions in symptoms of psychological problems (e.g., the Strengths and Difficulty Questionnaires) and improvement in school related self-efficacy from pre – 3-month follow-up compared to youths receiving TAU, with on average medium group effect sizes ( $d$ 's ranging from .29 to .58).

The theoretical approach of the B2S program is transdiagnostical, based on a modular CBT manual. The program aims at addressing both school attendance problems and mental health problems that are associated with SA. The intervention combines a functional and a CBT approach. The functional approach involves identifying the motivational function of the child's school absenteeism and includes 1) avoidance of school-based situations that provoke negative affectivity (anxiety/depression), 2) avoidance of aversive school-based social/evaluative situations, 3) pursuit of attention from significant others outside of school, and 4) pursuit of tangible reinforcement outside of school. The cognitive approach addresses prevalent negative cognitions in this group, e.g., cognitions concerning the youth's ability to cope with situations related to school attendance ([name] et al., 2019). Also, focus on increasing school related self-efficacy may reduce associated emotional and behavioural problems and promote reengagement with school.

## Scope of the research project

### Pilot study:

In Norway, there is a lack of a clear and systematic approach for helping children and youths with problematic SA. Developing effective interventions and procedures for helping children with SA is important. The ambition of the present study is to adapt a new and promising intervention, aiming to improve the help offered to children, youth and families struggling with problematic SA in Norway.

The Norwegian B2S study is developed in collaboration with [name] at the University of Aarhus, Denmark. The planned pilot study is a collaboration between researchers at all the four Regional Centre for Child and Youth Mental Health and Child Welfare (RKBU North, West, Middle and RBUP South/East), and at the University of Bergen, Stavanger, Norwegian University of Science and Technology (NTNU), UiT the Arctic University of Norway, and the University of Aarhus, Denmark.

In the pilot study, the B2S program will be tested and evaluated in eight municipalities in all regions in Norway. Data will be collected during the school term of 2022-23. Based on the experiences from the pilot study, the research group aims to develop a large-scale randomized control intervention study of B2S in Norway.

#### *Primary aims*

The pilot has several aims. One overall aim is to gain experience in using the Back 2 School program in Norwegian community school- and health services and to assess the feasibility of the program in those settings. Another aim is to prepare and establish resources and infrastructure for a larger intervention study, and to establish a well-functioning cooperation between researchers, research organizations, and municipalities in different regions. Also, questions regarding the process of implementation of the program in community service settings will be an important issue for the pilot study.

By using a mixed method approach we will combine quantitative and qualitative methods addressing the following research questions:

#### Quantitative:

1. What are the characteristics of youths with SA and their families?
2. What are the changes in school absence rate, school related self-efficacy, and psychological difficulties following the intervention?
3. What additional needs for interventions and services are identified at termination of the program?
4. What is the degree of drop out, and level of satisfaction with the B2S program among children, parents and teachers?

#### Qualitative:

5. How do children, youths and their caregivers experience the B2S program? In what ways has the intervention been helpful? Are there ways the program and service system should be changed to better fit the needs of the youth and families struggling with SA? What would be optimized treatment and services for this group?
6. How do the therapists experience working with the B2S program to help children and youth with problematic SA? How did the therapists experience the training, the manual and the supervision? Are there ways the program and service system should be changed to better fit the needs of the youngster and families struggling with SA? What do the therapists consider to be optimized treatment and services for this group?
7. How do school staff experience the B2S program and the extended school module?

Based on the findings from the pilot study we aim to answer the following questions:

- How should a larger-scale implementations study of the Back 2 School program be planned, optimized and conducted?
- What should be the treatment comparison condition?
- What is an optimal level of school involvement in B2S?

## Resources and timeline

Figure 1: Timeline of the pilot study in Norway

### Project period

Data for the pilot project will be collected during the schoolyear of 2022 -2023. The analysis of the results and writing of reports are planned for the autumn of 2023. During the same time the project group plans to write the application for funding of the national effectiveness and implementation study, the main study.

The training of the professionals teams in the B2S program will be given during the week from the 21st to the 25th of March 2022. Beforehand, the teams have recruited a case for the first implementation of the program (the rehearsal case). The project group recommends that the first implementation is conducted shortly after the week of training. The data collected during the rehearsal case will not be included in the database of the pilot. The teams will meet with the supervisor team weekly as soon as they start implementing the B2S.

From august 2022 through June 2023 each team will conduct the B2S program and collect data from two cases each.

### Methods:

#### Participants and settings:

16 youth (6-16 years of age) will be included in the pilot study. The study will be conducted in eight Norwegian municipalities. Each region (East, West, Middle, North) recruits one to two teams of professionals from their geographical area. The setting for the B2S intervention is within first line services in the municipalities that are imposed to provide services for the target group.

#### Inclusion/ exclusion

In the pilot study, the following inclusion criteria applies:

- 1) Youth enrolled in a public school within the municipality,
- 2) aged 6–16 years and in 1st to -10th grade (excluding second semester of the 10th grade),

- 3) having a level of school absenteeism above 10% during the last 3 months of school (excluding legal absence, e.g., permitted extra holidays),
- 4) The youth and at least one parent/caregiver understand and speak Norwegian sufficiently to participate in the intervention and complete questionnaires,
- 5) At minimum one of the parents is motivated for working on increasing the youth's school attendance,
- 6) The participating families are willing to record baseline levels of school absenteeism and to participate in assessment, intervention procedures, and follow-up assessment,
- 7) Written informed consent from caregiver with judicial parental rights and responsibilities (usually both parents) to take part in the B2S pilot study is obtained.
- 8) Youth with a diagnosis of autism spectrum disorders cannot be included in the pilot study (exclusion criteria). Also, youth in need of acute and/or more intensive specialist mental health services (e.g., due to suicidal risk, ongoing symptoms of psychosis, ongoing eating disorder) cannot be included.

## Design:

### *Quantitative study:*

The evaluation of changes in school absenteeism (primary outcome) of the B2S program will be conducted using a multiple - baseline across subjects' design comparing the individuals' baseline levels of school absenteeism with the level of absenteeism following participation in the B2S program. The structure of the multiple baseline design with 16 subjects is comprised of two treatment conditions, a baseline (control) and an intervention condition with  $N$  equally spaced measurement occasions (Hedges, Pustejovsky, & Shadish, 2013). Thus, each subject function as their own control. Changes in secondary outcome measures (psychological wellbeing, school related self-efficacy) are assessed through repeated measurement at pre- (T1), and post intervention (T2). Information regarding additional needs for interventions and services is registered at T2 and at the 3-month booster session (T3).

### *Qualitative study:*

In-depth interviews with 8-10 of the young people, their caregivers and school personnel concerning their experience with participating in the B2S program will be conducted. The interviews will explore questions concerning program specific evaluation, but also questions to identify important success criteria and obstacles to getting help from the intervention. Focus group interviews with professionals concerning feasibility of the B2S program within the system of care will be conducted.

## Procedure:

### *Professionals*

Each municipality forms a B2S Team consisting of three professionals. The teams will be interdisciplinary including both member(s) with a relevant health profession (clinical psychologist, medical doctor, health nurse, social educator) and member(s) within a pedagogical profession (teacher, special educator).

### *Training*

All professionals receive a 5-days training course comprising assessment measures and proceedings, case formulation and the Back 2 School manual. Following training, the teams will be given weekly supervision by an interdisciplinary team of supervisors, consisting of 1 CBT expert and one with educational professional background, to ensure adherence and quality in delivery. The B2S teams receive a total of 70 hours of training (35 hours) and supervision (estimated 35 hours) during the pilot study.

### *Recruitment*

The recruitment procedure for the Back2School pilot study is as follows:

1. The Back 2 School team in the communal service go through referrals to find students that can be relevant for inclusion to the pilot project.
2. Administrative personnel from the communal service send out information about the pilot students to relevant youths and families, together with other information concerning their referral to the service. In the information-brochure the contact information for setting up an information meeting about the B2S pilot project is provided. The families are encouraged to contact the service to set up an information meeting within a week from the time when they received the information.
3. If the family haven't contacted the service within 10 days, they will be assigned the communal service's ordinary measures.
4. When the family contact the communal service to schedule an information meeting the service find a time and place for the meeting with the family. Information regarding the project and consent is not presented on the telephone.
5. In the information meeting with the family the B2S team from the communal service present the B2S program, and the procedures for the pilot project.
6. The family get the "Informed consent to participate in the B2S – pilot study" ("Samtykkeskriv for deltakelse i B2S-pilotstudie") and are asked to contact the service within a week if they wish to consent to participate in the project.
7. When the informed consent is signed the student and caregivers receive the collection of questionnaires (T1) on paper, together with scheme for registering school absence to the youth and to the parents.
8. When the T1-questionnaires from the youth and both parents are returned to the B2S team they are archived in the communal service secure journal system.
9. The parents sign the communal service consent scheme to allow cooperation with the school.
10. When the consent to contact/cooperate with the school is signed, the B2S team contact the school to inform about the B2S, and to hand out the T1 questionnaire to the main teacher.
11. The B2S-teams of the communal services collect the questionnaires, and the person-identifiable information is removed (name and date of birth are removed). The questionnaires are sent to the local project coordinator for that region. To calculate scores according to standardized norms information regarding gender and age must be provided for each individual.

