## Ethical consideration:

Research on child and adolescent patients is one of the fields that require the most careful reflections on ethical issues. The study will be conducted in accordance with prevailing ethical standards, and approval from the Regional Ethic Committee (REK) and the Norwegian Centre for Research Data (NSD). The project will be run in line with The World Medical Association (WMA) Declaration of Helsinki. Before entering the pilot study, the families will receive oral and written information and sign an informed consent. The families will be informed that the participation in research is voluntary and that they can withdraw their consent at any point in time.

Families that do not consent to participate in the pilot study will be offered help from the same first line services, without delay, but will not be offered the B2S program. Families who consent to participate but want to withdraw from the data collection after the intervention is started will be offered to continue with the B2S program. Whenever children and youths are identified as in need of extended interventions after the B2S program, the project will provide help with necessary referrals and guiding.

Utility-risk assessments: Youths and families that are being asked to participate in the pilot study are all self-referred to first-line services within their municipality. They are selected from the referral list of the services and B2S is offered as one alternative to service as usual. The B2S program is a systematic and focused intervention involving both youths, parents/caregivers, and the school. Results from the Danish study showed that youths and caregivers involved in the B2S program reported more satisfaction with the service than youth and families receiving "treatment as usual". One risk of participating the B2S program is that it is an intensive intervention requiring motivation and effort over time from youth, caregivers, and the school. Some participants may find the B2S programme too demanding or may develop a need for other interventions (eg. Suicidality). In such instances, the team of professionals providing the service, and the project group, is responsible for helping them with referrals and guiding.

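### The team that delivers the programme decides which referrals hear about the pilot, with no order of approach and no screening count, so favourable selection is possible and uptake has no recorded denominator

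*Protocol*

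**What the plan says.** Recruitment, step 1, has the municipal Back2School team "go through referrals to find students that can be relevant for inclusion to the pilot project". Step 2 limits the mailing to the families so identified: "Administrative personnel from the communal service send out information about the pilot students to relevant youths and families". Step 3 covers silence: "If the family haven't contacted the service within 10 days, they will be assigned the communal service's ordinary measures". No step asks for non-responders or decliners to be counted.

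The Ethical consideration section describes the same route: "They are selected from the referral list of the services and B2S is offered as one alternative to service as usual".

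The target per team is small. Project period says that from August 2022 through June 2023 "each team will conduct the B2S program and collect data from two cases each". The Drop-out paragraph, in the section on the intervention and its delivery, has the team recruit a further case after a dropout, so that each team still ends with two completed cases.

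Inclusion/exclusion lists the eligibility criteria. Several are objective: public school, age and grade, absence above 10% in the last three months, no autism diagnosis. Others need judgement, notably that at least one parent is motivated, for which no measure or threshold is given.

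The primary aims include "to assess the feasibility of the program in those settings". The quantitative questions cover participant characteristics, change, and dropout and satisfaction. The pilot is also meant to inform how a larger study should be planned.

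**The concern.** The people who choose whom to inform are the people who will treat, and they have a small quota counted in completed cases. A family that leaves costs the team a second recruitment. That gives a reason, conscious or not, to start with families who look likely to stay, and the written procedure does nothing to prevent it.

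If this happened, the answers on characteristics, change, dropout and satisfaction would describe chosen families rather than the eligible referrals that a larger study would have to recruit. The design has no concurrent comparison group, since each youth serves as their own control, so such selection would not show in the outcome data. Without counts of eligible and informed families, the pilot would also not be set up to say what share accepts the offer, which is a basic input for planning recruitment.

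**Working it through.** **1. The plan's own number.** Inputs: "The study will be conducted in eight Norwegian municipalities" (Participants and settings), one team per municipality (Professionals), two cases per team (Project period). Then 8 × 1 × 2 = 16, which matches "16 youth (6-16 years of age) will be included in the pilot study". The quota of two per team therefore drives the sample size.

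**2. What the quota means with replacement.** The target is 16 completers, so the number who start may exceed 16. No dropout rate is given. With an assumed dropout proportion d, the expected number of starters is 16 / (1 − d):

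| Assumed d | 16 / (1 − d) | Starters, rounded up |
|---|---|---|
| 10% | 17.8 | 18 |
| 20% | 20.0 | 20 |
| 30% | 22.9 | 23 |

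Dropout must therefore be reported over all starters. Over the final 16 it would be zero by construction.

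**3. How far selection could move an outcome.** Assumption: a team has m eligible referrals, ranks them on a judgement that correlates r with the outcome, and takes the best two. The expected shift in SD units is r × (expected mean of the two largest of m standard normal values). That mean was obtained by simulation with 400,000 replicates.

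| m | Mean of top two | r = 0.1 | r = 0.3 | r = 0.5 |
|---|---|---|---|---|
| 2 | 0.00 | 0.00 | 0.00 | 0.00 |
| 3 | 0.42 | 0.04 | 0.13 | 0.21 |
| 4 | 0.66 | 0.07 | 0.20 | 0.33 |
| 6 | 0.95 | 0.10 | 0.29 | 0.48 |
| 10 | 1.27 | 0.13 | 0.38 | 0.64 |

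Neither m nor r is in the protocol. With two eligible referrals per team the effect is nil.

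**4. The same mechanism on dropout.** Assume that the more promising half of referrals completes with probability 0.9 and the rest with 0.6.
- Without selection, completion is (0.9 + 0.6) / 2 = 0.75, so dropout is 25% and 16 / 0.75 = 21.3 starters are expected.
- If teams took only the promising half, completion is 0.9, dropout is 10% and 16 / 0.9 = 17.8 starters are expected.

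This is an upper illustration, because it supposes that teams identify the better half without error. Selection lowers dropout.

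**5. What an uptake rate would be worth if counted.** Taking 16 consenters and an assumed number of families informed, with exact 95% intervals:

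| Informed (assumed) | Uptake | 95% interval |
|---|---|---|
| 20 | 80% | 56 to 94% |
| 32 | 50% | 32 to 68% |
| 64 | 25% | 15 to 37% |
| 100 | 16% | 9 to 25% |

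The intervals are wide, but they separate an 80% uptake from a 25% one, which is a useful distinction for planning.

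**The case against.** The strongest reply is that relevance for inclusion most naturally means meeting the inclusion criteria, so step 1 describes ordinary eligibility screening. The sentence in Ethical consideration fits that reading equally well. Families must also make contact, attend a meeting and consent, and a motivated parent is an openly declared criterion, so a motivated sample is partly the intended population. Because each youth is their own control, selection bears mainly on how far the results generalise. Uptake is not a stated research question.

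Much of this stands. A reader might infer that the protocol licenses hand-picking, or that the sample will be therapist-selected. The text does not go that far: it leaves the choice among eligible families open and does not grant it. A reader might also infer that uptake could never be calculated. That is too strong, because the services hold the referral lists and might rebuild the counts. Some protocol text between the school module and User representatives was not available for this review, so a log described there cannot be excluded.

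The reply does not supply a definition of relevance, an order of approach or a required tally. Family opt-in acts only after the team has settled who is informed. These are recruitment rules, which belong in the protocol and are not commonly left to a statistical analysis plan.

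**Conclusion.** The point holds as a correctable weakness in the recruitment procedure. Bias is possible and has not been shown. It needs a team with more than two eligible referrals and some ability to foresee who will finish. If both hold, change and satisfaction would look better and dropout lower than among eligible referrals in general. It would be wrong to conclude that all three measures would be pushed upward.

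The size cannot be fixed from the protocol. The 0 to 0.64 SD range and the 25% versus 10% dropout contrast rest entirely on the assumptions stated with them. The missing uptake denominator is a gap in what must be recorded, and it matters because the pilot is meant to inform a larger study. For a 16-case pilot this is a worthwhile improvement and no threat to the study's validity.

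**What to change.** Amend Recruitment step 1 as follows.

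- Define a relevant referral as one that meets those criteria in Inclusion/exclusion that can be judged from the referral itself. Criteria that need contact with the family, such as parental motivation, are assessed later and the result is recorded.
- Send the information to all such referrals in order of referral date, in small batches if needed to limit delay, until the team's places are filled. Places include any replacement required by the Drop-out paragraph.
- Keep a one-page tally per team: referrals screened, eligible, informed, responding within 10 days, declining (with the reason if offered), consenting and dropping out.
- Report dropout over all who started, including those later replaced.

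The planned number stays at 16 completed cases. The cost is a few sentences of protocol text and the tally. Teams lose discretion over whom to approach first. Recruitment may be slightly slower, since each approach can take up to 10 days for a reply, then a meeting, then up to a week for consent. The uptake rate from about 16 consenters will be imprecise and should be reported with its interval.
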